5.2 Treatment Assignment Procedures

5.2.1 Randomized Procedure

This is a partially double-blind, randomized controlled trial with an enrollment target of 825 infants who will be allocated to one of the two groups at a ratio of 2:1 to receive the liquid formulation of

Confidential

ROTAVIN or the frozen formulation (ROTAVIN-M1). Permuted block randomization will be used to generate the randomization schedules for the study. The randomization will be stratified by study site and study team and the block size for each part will be chosen based on the number of treatment groups, randomization ratio and anticipated enrollment size at each study site. Infants will be randomized sequentially in the order that they are enrolled at the site by the team.

The randomization list that contains a participant identification number and the corresponding randomization assignment will be generated using computer software by an independent statistician who is not involved in conduct or analysis of the study. Prior to study initiation it will be provided to the data management team to setup the randomization system

Each participant will be assigned a unique screening number by the investigator after signing the informed consent. He/she will be assigned a participant identification number once he/she is enrolled. The Investigator will maintain the screening/enrollment log. The log will contain essential information including screening number, date of screening, gender, date of birth, whether or not the potential participant meets eligibility criteria, whether participant is enrolled, participant identification number (if he/she in enrolled) and if not, reason for not enrolling.

Once a participant identification number has been assigned to a participant, it will not be used again. Additional participants may be randomized into the study at the discretion of the sponsor in the case of any participant who is randomized but does not receive any study vaccine.

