12.4.2 Analysis of primary objectives

Analysis of primary immunogenicity objective

The GMCs of serum anti-rotavirus IgA antibody concentrations at 28 days after the second dose of ROTAVIN or ROTAVIN-M1 will be calculated along with its two-sided 95% CI, by exponentiation of the corresponding log10-transformed mean and its two-sided 95% CI limits.

To compare the immunogenicity of ROTAVIN and ROTAVIN-M1 at 28 days following the second dose of the study vaccine, the following hypothesis will be tested,

H₀: GMC_{ROTAVIN} / GMC_{ROTAVIN-M1} $\leq \frac{1}{2}$

H1: GMC_{ROTAVIN}/ GMC_{ROTAVIN-M1} > $\frac{1}{2}$

The test will be done at 28 days following the second dose of ROTAVIN and ROTAVIN-M1 and will be conducted with one-sided with a type I error rate of 0.025. The ratio of the post-vaccination anti-rotavirus IgA GMCs between the ROTAVIN and ROTAVIN-M1 groups will be provided with its two-sided 95% CI. The log₁₀-transformed anti-rotavirus IgA concentrations will be used to construct a two-sided 95% CI for the mean difference between the two study groups using t-distribution. The mean difference and corresponding 95% CI limits will be exponentiated to obtain the GMC ratio and the corresponding 95% CI. If the lower limit of the 95% CI of the ratio of GMCs between the ROTAVIN and ROTAVIN-M1 groups is larger than 1/2, the liquid formulation of ROTAVIN is considered to be non-inferior to the licensed frozen formulation of the vaccine (ROTAVIN-M1). Serum anti-rotavirus IgA antibody concentration below the lowest limit of quantitation (LLOQ) (i.e. below the starting dilution of assay recorded as "<LLOQ") will be set to half that limit (i.e. LLOQ/2). In case of that the concentration is above the upper limit of quantitation (ULOQ), an actual value reported will be used.

The comparison of the GMCs between the two study vaccines will also be performed using analysis of covariance (ANCOVA) method with log_{10} -transformed anti-rotavirus IgA concentrations as the dependent variable, the vaccine group as the explanatory variable, and log_{10} -transformed baseline concentrations as a covariate. This adjusted analysis will be considered as supportive.

Analysis of primary safety objective

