The number and percentage of participants experiencing solicited post-vaccination reactogenicity (fever, diarrhea, vomiting, decreased appetite, irritability, decreased activity level) during the 7-day period after each vaccination will be tabulated by vaccine group and severity. For the percentage, an exact two-sided 95% CI will be provided using Clopper-Pearson method.

The percentage of participants with at least one solicited post-vaccination reactogenicity between ROTAVIN and ROTAVIN-M1 groups after each vaccination will be compared using a two-sided Fisher's Exact test with a significance level of 0.05.

12.4.3 12.4.3 Analysis of secondary objectives

Analysis of secondary immunogenicity objectives

The percentage of participants with seroconversion and seropositivity 28 days after the second vaccination will be computed for the ROTAVIN and ROTAVIN-M1 groups along with exact two-sided 95% CIs based on Clopper-Pearson method. The difference in the percentage between the two groups will be provided along with its two-sided 95% CI obtained by Miettinen and Nurminen method.

In addition, a reverse cumulative distribution (RCD) curve for anti-rotavirus IgA concentrations will be created by vaccine group and visit.

Analysis of secondary safety objectives

The number and percentage of participants experiencing immediate adverse events within 30 minutes after each vaccination, unsolicited AEs four weeks after each vaccination and SAEs including intussusception reported through 4 weeks after the last vaccination will be provided by vaccine group, severity, and causality. For the percentage, an exact two-sided 95% CI will be provided using Clopper-Pearson method.

The original verbatim terms used by investigators to identify adverse events on case report forms (CRFs) will be coded according to MedDRA dictionary. AEs including SAEs will be summarized and classified by SOC and preferred term of the MedDRA dictionary. They will be displayed by vaccine group as both frequencies and percentages.

The analysis of unsolicited adverse events comprises the following categories:

- Any unsolicited AEs;
- Related unsolicited AEs;
- SAEs;
- Related SAEs;
- Unsolicited AEs leading to withdrawal from the study;
- Unsolicited AEs leading to withdrawal from study vaccination but remaining in the study;
- Unsolicited AEs leading to hospitalization;

• Any AEs leading to death.

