4.3.2 Method of Assigning Participants to Vaccine groups (Randomization)

The study will be conducted in the Nam Dinh and Quang Ninh provinces in Vietnam. Randomization and all study related activities will take place at approximately 12 commune health centers associated with one of the sites, and not at the sites. Within each site, the commune health centers will be divided into two independent teams, Team 1 and Team 2.

A manual randomization process will be used. Randomization will be stratified by site and team using a permuted block design. The unblinded team at the CRO will create two sealed opaque envelopes for each participant. When an infant is randomized, the seal of the envelope infant's participant ID is broken, and the vaccine with the code given inside the envelope is administered to the participant by the unblinded vaccine administrator. After vaccination, the envelope will be resealed and sent back to the site for data entry. The unblinded site staff will re-open the envelope

to enter the data into Advantage eClinicalSM. After data entry, the envelope will be resealed and kept in a secure locker at the site.

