46.	Immunogenicity result not available	Serological results unavailability	Serological results not available for any of the sampling timepoint (including lost samples, blood sample not done, unable to test, absence of parallelism).	No data review. This exclusion will be filtered at "Analysis Level"	Exclude
47.	Study vaccine administration	Vomiting after repeat dose administration	Subjects who had vomiting/regurgitation within 5 minutes of repeat dose vaccine administration	No data review. This exclusion will be filtered at "Analysis Level"	Exclude

10. Prior and Concomitant Medications

All medications taken since birth are recorded. *Prior medications are defined as those medications taken prior to Day 1 and not continued to be taken on or after Day 1; concomitant medications are defined as those medications continued to be taken or newly initiated on or after Day 1.* All medications will be coded using World Health Organization (WHO) Drug Dictionary.

Prior will be summarized by the anatomical-therapeutic component (ATC) levels 1 and 3 (Table 9). Concomitant medications will be summarized by ATC levels 1 and 3 after any dose and after each dose (Table 10-12). Results will be tabulated for the safety population by the vaccine group and overall. All medications will be listed with concomitant medications separately identified (Listing 8).

Concomitant vaccinations will be summarized by vaccination. Results will be tabulated for the safety population for each vaccine group and overall (Table 13). All EPI vaccinations will be listed (Listing 9).

11. Primary Analyses

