12.1 Immunogenicity

GMC along with the two-sided 95% CI is calculated by exponentiation of the anti-log of the arithmetic mean of the \log_{10} -transformed concentrations. GMC along with the two-sided 95% CI for IgA at baseline and 28 days after the second vaccination will be summarized descriptively by vaccine group for the PP and FA population (Tables 14 and 15, respectively).

Non-inferiority in the immunogenicity of ROTAVIN in comparison to ROTAVIN-M1® is defined as the ratio of GMCs between ROTAVIN and ROTAVIN-M1® is larger than 1/2. The following hypothesis will be tested:

$$H_0: \text{GMC}_{\text{ROTAVIN}}/\text{GMC}_{\text{ROTAVIN-M1}} \leq \frac{1}{2}$$

$$H_1: \text{GMC}_{\text{ROTAVIN}}/\text{GMC}_{\text{ROTAVIN-M1}} > \frac{1}{2}$$

The ratio of GMCs between ROTAVIN and ROTAVIN-M1® along with the two-sided 95% CI is calculated using the log₁₀-transformed anti-rotavirus IgA concentrations to construct a two-sided 95% CI for the mean difference between the two study vaccines using the t-distribution. The mean difference and corresponding 95% CI are exponentiated to obtain the GMC ratio and the corresponding 95% CI. If the lower limit of the 95% CI of the ratio of GMCs between ROTAVIN and ROTAVIN-M1® is larger than 1/2, ROTAVIN is considered to be non-inferior to ROTAVIN-M1®. This results in a one-sided type I error rate of 0.025.

The ratio of the GMCs 28 days after the second dose will be provided along with the two-sided 95% CI for the PP and FA population (Tables 14 and 15, respectively).

The non-inferiority test on the 95% CI for the ratio of GMCs on the PP population is considered the primary analysis. The remaining immunogenicity analyses are considered supportive.

If the serum anti-rotavirus IgA antibody concentration is below the lower limit of quantitation (LLOQ), i.e. assay is recorded as “<LLOQ”, then the concentration will be set to half that limit (LLOQ/2). If the concentration is above the upper limit of quantitation (ULOQ), an actual value will be reported.

An analysis of covariance (ANCOVA) model with the log₁₀-transformed concentrations as the dependent variable, the vaccine group as the explanatory variable, and the log₁₀-transformed baseline concentrations as a covariate will also be performed for the PP and FA population (Tables 14 and 15, respectively). This adjusted analysis will be considered as supportive.

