12.2 Safety

The number and percentage of participants experiencing solicited post-vaccination reactogenicity (fever, diarrhea, vomiting, decreased appetite, irritability, decreased activity level) during the 7-day period after any dose will be tabulated by vaccine group and severity (Table 16). For the percentage within each group, an exact two-sided 95% CI will be provided using Clopper-Pearson method. The percentage of participants with at least one solicited post-vaccination reactogenicity between ROTAVIN and ROTAVIN-M1® groups after both doses and after each vaccination will be compared using a two-sided Fisher's Exact test with a significance level of 0.05. Results will be tabulated for the safety population for participants with available data. These results will be repeated after each dose (Tables 17 and 18) and are considered as supportive.

Solicited reactions will be presented by severity for each vaccine group after any vaccinations and after each vaccination (Figure 2-4).

Solicited reactions will be listed (Listing 11). Separate listings will be presented for solicited reactions ongoing on day 7 (Listing 12) and severe solicited reactions (Listing 13).

12. Secondary Analyses

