Listing 7: Participants Excluded from Analysis Population

Treatment	Site	Participant ID	Analyses in which Participant is Included	Analyses from which Participant is Excluded	Results Available?	Reason Participant Excluded
ROTAVIN	Nam Dinh	xxx	[e.g. Safety]	[e.g. Safety]		xxx
...						
ROTAVIN	Quang Ninh	xxx	[e.g. Safety, FA, PP]	[e.g. Safety, FA, PP]	Yes	xxx
...						

Note: Participants from Nam Dinh will be analyzed for inclusion in the safety population only since serum samples were not collected.

“Yes” in the “Results available” column indicates that available data were removed from the immunogenicity analyses. “No” indicates that no data were available for inclusion in the analysis.

Listing 8: Prior and Concomitant Medications – Safety Population

Treatment	Site	Participant ID	When Medication was taken ^a	Medication	WHO Drug Dictionary ATC Level 3	WHO Drug Dictionary ATC Level 1	Indication	Start Date	End Date	Days Relative to Enrollment		Duration (Day)	Dose (Units)	Frequency	Route
										Start Date	End Date				
ROTAVIN	Nam Dinh	xxx	xxx	xxx	xxx	xxx	Medical history (M1)	DDMMYY	DDMMYY	xxx	xxx	xxx	2 mg	xxx	xxx
		xxx	xxx*	xxx	xxx	xxx	Adverse Event (A1)	DDMMYY	DDMMYY	xxx	xxx	xxx	1 tablet	xxx	xxx
		xxx	xxx*	xxx	xxx	xxx	Solicited reaction	DDMMYY	DDMMYY	xxx	xxx	xxx	xxx	xxx	xxx
		xxx	xxx	xxx	xxx	xxx	xxx	DDMMYY	DDMMYY	xxx	xxx	xxx	xxx	xxx	xxx
		xxx	xxx	xxx	xxx	xxx	xxx	DDMMYY	DDMMYY	xxx	xxx	xxx	xxx	xxx	xxx
ROTAVIN-M1	Nam Dinh	xxx	xxx	xxx	xxx	xxx	xxx	DDMMYY	DDMMYY	xxx	xxx	xxx	xxx	xxx	xxx
		xxx	xxx	xxx	xxx	xxx	xxx	DDMMYY	DDMMYY	xxx	xxx	xxx	xxx	xxx	xxx

^aConcomitant medications are indicated with an asterisk (*)

Programming note: if response to type of indication is “Medical history” or “Adverse Event”, then print the event code in parenthesis; if response to dose units, frequency, or route is “Other”, then print the specify details in parenthesis.

Listing 9: Concomitant Vaccinations – Safety Population

Treatment	Site	Participant ID	Vaccine Name	Date of Vaccination	Days from Enrollment	Route	Site
ROTAVIN	Nam Dinh	xxx	xxx	DDMMYY	xxx	xxx	xxx
		xxx	xxx*	DDMMYY	xxx	xxx	xxx
		xxx	xxx	DDMMYY	xxx	xxx	xxx
		xxx*	xxx*	DDMMYY	xxx	xxx	xxx
		xxx	xxx	DDMMYY	xxx	xxx	xxx
ROTAVIN-M1	Nam Dinh	xxx	xxx	DDMMYY	xxx	xxx	xxx
		xxx	xxx	DDMMYY	xxx	xxx	xxx

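### The primary analyses leave out the randomization strata and the baseline IgA, and the primary safety comparison gives a p-value with no between-group interval

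*SAP*

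**What the plan says.** **Randomization.** Protocol 5.2.1 states: "The randomization will be stratified by study site and study team". SAP 4.3.2 agrees, "Randomization will be stratified by site and team using a permuted block design", and sets two teams per site. That makes four strata in the whole trial and two within Quang Ninh.

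**Primary GMC analysis.** Serum is taken only at Quang Ninh; the note to SAP Listing 7 reads "Participants from Nam Dinh will be analyzed for inclusion in the safety population only since serum samples were not collected". Protocol 12.4.2 declares non-inferiority "If the lower limit of the 95% CI of the ratio of GMCs between the ROTAVIN and ROTAVIN-M1 groups is larger than 1/2". The interval is a two-group t interval on log10 concentrations with no covariates, and SAP 12.1 makes the per-protocol (PP) population primary. An ANCOVA with vaccine group and log10 baseline is also planned: "This adjusted analysis will be considered as supportive".

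**Baseline availability.** SAP Table A2, row 46, excludes infants from PP on the ground "Serological results not available for any of the sampling timepoint".

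**Primary safety analysis.** Protocol 12.4.2 has the percentages with at least one solicited reaction in the two "groups after each vaccination will be compared using a two-sided Fisher's Exact test with a significance level of 0.05". SAP 12.2 makes the any-dose comparison primary and the per-dose ones supportive. On intervals, SAP 12.2 says: "For the percentage within each group, an exact two-sided 95% CI will be provided using Clopper-Pearson method". The only between-group column in the Table 16 shell is the Fisher p-value. For seroconversion and seropositivity, SAP 13.1 does plan a difference with a Miettinen-Nurminen interval.

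**The concern.** An analysis normally reflects the factors on which randomization was stratified, and it uses a baseline measurement of the outcome where one is complete. Here the baseline value is a condition of PP membership, yet the decisive test never uses it. What is lost is precision; type I error is not inflated.

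The safety side has the more practical gap. The primary objective is comparative, but the planned output gives neither the excess in reactions nor a bound on it. A non-significant Fisher p-value could then be taken to mean equal reactogenicity when the data still allow a sizeable excess.

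**Working it through.** **1. Reproduce the GMC power (Protocol 12.2).** Inputs: n = 250 and 125, SD 0.8 on log10, margin 0.5, one-sided alpha 0.025, true ratio 1.
- SE = 0.8 × √(1/250 + 1/125) = 0.0876
- Non-centrality = log10(2)/SE = 0.30103/0.0876 = 3.435, with 373 df
- Power = 92.9% (stated 93%)
- 95% half-width = 1.966 × 0.0876 = 0.172 log10, a factor of 1.49

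SDs of 0.75 and 0.70 give 95.5% and 97.5% (stated 95% and 97%).

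**2. Is baseline complete in PP?** The full analysis population already requires at least one evaluable sample (SAP 7.1). Row 46 therefore removes someone only if it means a result missing at either time point. On that reading every PP infant has a baseline value, and adjustment loses nobody. This does not carry over to the full analysis population.

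**3. Gain from baseline.** Protocol Table 2.11 gives a pooled pre-vaccination GMC of 5.72 (95% CI 5.5 to 5.9, n = 600).
- SD = [log10(5.9) − log10(5.5)]/2 × √600/1.964 = 0.19. Phu Tho alone gives 0.255.
- R² = (slope × baseline SD/0.8)². The slope is not in the documents; 0.5 to 1 is assumed.
- The residual SD is 0.8 × √(1 − R²).

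| Baseline SD | Slope | R² | Power | Interval narrower by |
|---|---|---|---|---|
| 0.19 | 0.5 | 1.4% | 93.2% | 0.7% |
| 0.19 | 1 | 5.7% | 94.2% | 2.9% |
| 0.255 | 0.5 | 2.5% | 93.5% | 1.3% |
| 0.255 | 1 | 10.2% | 95.1% | 5.2% |

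**4. Gain from team.** With equal-sized teams, R² = d²/(4 × 0.64). Assumed differences d of 0.05 and 0.10 log10 give R² of 0.1% and 0.4%, and power of 92.9% and 93.0%: at most 0.1 point.

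**5. Safety power.** Exact enumeration for Fisher at 5% versus 11.8% (275 versus 550) gives 90.8% (stated 90%), with an actual size of 0.040 at 5% in both groups. The comparison with a Cochran-Mantel-Haenszel (CMH) test over four site-by-team strata comes from simulation, with assumed stratum sizes of 150/75, 150/75, 126/63 and 124/62 and an excess of 6.8 points in every stratum:

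| Comparator rate at the two sites | Fisher | Pooled chi-square | CMH |
|---|---|---|---|
| 5% / 5% | 90.9% | 91.6% | 91.6% |
| 5% / 10% (assumed) | 83.6% | 84.6% | 84.7% |
| 5% / 25% (assumed) | 66.1% | 67.7% | 70.2% |

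The step from Fisher to chi-square reflects Fisher's discreteness. Only the step from chi-square to CMH comes from stratification.

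**6. What the missing interval would show.** Illustrative counts: 44/550 = 8.0% and 14/275 = 5.1%, a difference of 2.9 points. Fisher p = 0.1485. The Miettinen-Nurminen 95% interval is -0.9 to +6.2 points. The upper limit is close to the 6.8-point difference used for sizing in Protocol Table 12.2, yet the planned table would show only a non-significant p-value.

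**The case against.** - **The tests are valid and match the powering.** True. The unadjusted t-test and Fisher's test are the ones used in Protocol 12.2. The efficiency point alone would be optional.
- **The adjusted ratio is already planned.** True. The Table 14 shell prints it beside the unadjusted ratio, so for baseline the change is mainly which result decides. Team is still absent from that model.
- **The GMC gain may be even smaller.** This stands. Table 2.11 also implies a post-vaccination SD of about 0.71 (85.9, 95% CI 74.5 to 99.1, n = 503), at which unadjusted power is already about 97%. Rounding of the published limits lets the baseline SD lie anywhere from 0.14 to 0.24. With 94.3% of infants below 20 before vaccination in the earlier phase III trial, baseline could be nearly constant and the gain close to zero.
- **Row 46 is loosely worded.** It is, and row 29 separately excludes a missed post-vaccination sample, so the two rows overlap. The either-time-point reading is still the only one that gives row 46 any effect.
- **No site difference in reactogenicity is documented.** Correct. The 5%/25% case is hypothetical, and at the planned 5% stratification adds about nothing.
- **A reader can subtract the percentages.** A crude interval can be built from the printed counts, but it would be post hoc, and a stratified one cannot be recovered from Table 16. The objection does not remove the gap.
- **Changing the primary analysis is not free.** It needs an amendment and approvals. It costs no data and no PP participants, and a route through the SAP alone exists.

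**Conclusion.** The point holds as an improvement, not as a correction. On the GMC side the gain is 0.3 to 1.3 power points at the pooled baseline SD, or up to 2.2 points at the wider Phu Tho spread. It rests on assumed slopes of 0.5 to 1 and the planned SD of 0.8, and shrinks if the SD is nearer 0.71. On the safety side stratification matters only if the sites differ substantially. The missing between-group estimate and interval is the part most worth acting on, because it concerns a primary objective and the SAP already uses a suitable method for secondary endpoints.

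One limit on the validity statement: the SAP does not say whether the t interval pools the variances. If the SDs were 0.7 (ROTAVIN) and 0.8 (ROTAVIN-M1), simulated one-sided size is about 0.031 pooled and 0.026 with Welch's method. The pooled-variance ANCOVA gives about 0.030, so adjustment would not change this.

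**What to change.** Before database lock, in Protocol 12.4.2 and SAP 12.1 and 12.2:

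- **GMC.** Make the primary analysis the linear model of log10 Day 85 IgA on vaccine group, team and log10 baseline in PP. Declare non-inferiority if the lower 95% limit of the adjusted ratio exceeds 0.5. Keep the unadjusted t interval as supportive.
- **Safety.** For participants with at least one solicited reaction, report a CMH test stratified by site and team, and a stratified Miettinen-Nurminen risk difference with its 95% CI. Add that column to Tables 16 to 18.

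This takes matching edits to both documents and to the shells of Tables 14 to 18, plus the sponsor and ethics approvals in Protocol section 16. No new data are needed.

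**Fallback without a protocol amendment.** Add team to the supportive ANCOVA and report the stratified risk difference with its interval as supportive. This needs SAP text and table shells only, and leaves the non-inferiority rule and the Fisher test as they are.
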